1. STUDY OBJECTIVES AND ENDPOINTS

1.1. Primary and Secondary Study Objectives

The primary objective of this study is to evaluate safety and tolerability of pridopidine in patients with Huntington's disease (HD).

The secondary objectives of the study are to assess the effects of long-term, open-label dosing with pridopidine on motor symptom severity, overall patient function, physical performance, and health-related quality of life in patients with HD.

1.2. Study Endpoints

1.2.1. Safety Endpoints

The safety endpoints for this study are as follows:

- adverse events (AEs) throughout the study
- vital signs assessments
- concomitant medication usage throughout the study
- physical examination findings
- clinical laboratory evaluations (hematology, clinical chemistry, and urinalysis)
- electrocardiogram (ECG) findings
- Suicidality [using the Columbia-Suicide Severity Rating Scale (C-SSRS)] and Problem Behaviors Assessment-Short form (PBA-s)

1.2.2. Tolerability Endpoints

The tolerability endpoints for this study are as follows:

- Proportion of subjects (%) who prematurely discontinued from the study
- Proportion of subjects (%) who prematurely discontinued from the study due to AEs

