A referral for psychiatric evaluation is required for AE/SAE of suicidal ideation/suicidal attempt or significant increase in the suicidality scale from baseline (e.g., 2 point increase or higher) or C-SSRS or PBA-s suicidality score 3 and above. All patients with PBA-s suicidal ideation item score >2 (ie, 3, 4, 5) will be discontinued from treatment with study drug. Patients who are discontinued from treatment may continue their participation in the study and perform the scheduled visits and assessments, while off study drug. They will continue to be closely monitored by the investigator and will be referred for psychiatric evaluation per the investigator's medical judgment. Where possible, the same person should act as a patient’s caregiver/informant throughout the study. If this is not possible, a patient should have no more than 2 caregivers/informants throughout the study. All possible attempts should be made to assure that the caregiver/informant will attend the clinical visits in person together with the patient. If the caregiver/informant is not available to attend the clinic visit, the interview can be done over the phone.

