All patients will be treated with study drug during the course of the study. After the 1 week titration period, patients will be seen at weeks 4, 12, 26, 52, 78, and every 26 weeks thereafter. An EoS follow-up visit will take place 2 weeks after end of treatment visit. Safety evaluation telephone calls will be performed at weeks 18, 38, and every 26 weeks thereafter. The alternating safety visits and telephone contacts (TCs) result in a safety assessment frequency of approximately every 3 months throughout the entire study duration. The safety TCs must be conducted by the study investigator. During these phone calls, inquiries about adverse events, concomitant medication (including changes in use of benzodiazepines and antidepressants), changes in use of alcohol and illicit drugs, C-SSRS, and an abbreviated PBA-s (a subset of PBA-s questions on depressed mood, suicidal ideation, anxiety, irritability, loss of motivation, and obsessive-compulsive behaviors) will be conducted.

During the TCs, if the patient receives a score of 0 on the C-SSRS and PBA-s suicidal ideation assessments, the subsequent safety TCs will remain as scheduled as long as the scores of 0 are unchanged. If the patient receives a score of 1 or 2 on the C-SSRS or PBA-s suicidal ideation assessments, the safety TCs will be conducted every 4 weeks to monitor the patient's status until the scores change to 0 (after which the frequency of safety TCs will revert back as scheduled, as described above). Patients with a C-SSRS ideation score of 3 and above or a PBA-s suicidality

score of 3 and above, and all patients with C-SSRS suicidal attempts or acts (behavior), will be discontinued from treatment with study medication and will be referred to a psychiatrist for further evaluation and assessment, and handled as described in Section 6.1.5. of the protocol.

For patients with a C-SSRS or PBA-s score of 1 or 2, if in the judgment of the investigator, the patient is not in good mental health during an in-clinic visit or safety TC, the frequency and the methods for monitoring may be changed (ie, more frequent visits or TCs may be added as deemed necessary, or the patient can be referred to a psychiatrist for additional evaluation and treatment and will be monitored until recovery or their condition stabilizes, in accordance with the instructions provided in Section 6.1.5 and Section 7.8.1 of the protocol.

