Patients who discontinue study medication due to safety or tolerability reasons may continue in the study off drug and perform the scheduled visits and assessments.

[figure not shown]
Patients who withdraw from the study will have the early termination procedures and assessments performed at their final visit.

An independent internal safety committee will oversee the study (see Section 3.6.1 of the protocol).

Digital Health Sub-study (optional participation):

Motor symptoms can be objectively assessed in HD patients using different quantitative motor assessments.

Objective motor assessments aim at improving the limited sensitivity observed with categorical clinical rating scales, and reducing the intra- and inter-rater variability, as well as potential placebo effect observed in scales such as the UHDRS. Improved sensitivity for early-stage clinical studies of efficacy of a new drug on motor dysfunction is expected with objective assessments and may support early go/no go decisions in smaller cohorts of patients.

Study procedures and assessments are outlined in Table 1 of the sub-study protocol.

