5.2. Patient Disposition

Patient screened, patients screened but not in the ITT analysis set (and reason not in the ITT analysis set) will be summarized using patient counts. Patients in the ITT analysis set, patients in the ITT analysis set but not treated, patients in the safety and full analysis sets, patients who completed treatment and completed study, and patients who withdraw from the treatment and study (and reasons for withdrawing) will be summarized using descriptive statistics.

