7.3. Adverse Events

All AEs will be coded using the MedDRA. AEs occurring on or after the first day of study drug administration will be included in the summaries. Summaries will be presented for all AEs (overall and by severity), AEs determined by the investigator to be related to study drug (overall and by severity), serious AEs, AEs leading to withdrawal from the study, and non-serious AEs.

The incidence and total number of AEs will be summarized using descriptive statistics by SOC and PT (all AEs overall will also be presented by just PT category). For the incidence of AEs, patients are counted only once in each SOC category, and only once in each PT category. The exposure adjusted incidence rate will also be presented and is defined as the number of patients with an AE divided by patient-years of treatment. For calculating patient-years, patients with an AE contribute with treatment exposure up to the day of their first AE, and patients without an AE contribute with the entire treatment exposure. For the summary by severity, patients are counted at the greatest severity. AEs missing relationship to study drug will be included in the study drug related summary.

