8. TOLERABILITY VARIABLES AND ANALYSIS

Tolerance is summarized with the safety analysis.

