9. STATISTICAL SOFTWARE

All data listings, summaries, and statistical analyses will be generated using SAS[®] version 9.4 or later.

**10. CHANGES TO ANALYSES SPECIFIED IN THE STUDY
PROTOCOL**

There are no changes to analyses specified in the study protocol.

**APPENDIX A. MODIFIED PHYSICAL PERFORMANCE TEST (MPPT)
SCORING METHOD**

| No. | Task | Items Score Values |
|-----|--|---|
| 1. | Balance Tasks | 
Standing Balance Feet Together
 
 • ≥ 10 sec = 1 • 0 - <10 sec or Unable = 0 
Standing Balance Semi Tandem
 
 • ≥ 10 sec = 1 • 0 - <10 sec or Unable = 0 
Standing Balance Tandem
 
 • ≥ 10 sec = 2 • 3 - <10 sec = 1 • 0 - <3 sec or Unable = 0 |
| 2. | Chair rise | 
 • >0 - 11 sec = 4 • >11 - 14 sec = 3 • >14 - 17 sec = 2 • >17 sec = 1 • 0, Unable = 0 |
| 3. | Lift a book and put it on a shelf | 
 • >0 - 2 sec = 4 • >2 - 4 sec = 3 • >4 - 6 sec = 2 • >6 sec = 1 • 0, Unable = 0 |
| 4. | Put on and remove a jacket (sum of time to put and to remove the jacket) | 
 • >0 - 10 sec = 4 • >10 - 15 sec = 3 • >15 - 20 sec = 2 • >20 sec = 1 • 0, Unable = 0 |
| 5. | Pick up a penny from floor | 
 • >0 - 2 sec = 4 • >2 - 4 sec = 3 • >4 - 6 sec = 2 • > 6 sec = 1 • 0, Unable = 0 |
| 6. | Turn 360 degrees | 
Steps
 
 • Continuous = 2 • Discontinuous = 0 
Steadiness
 
 • Steady = 2 • Unsteady (grabs, staggers) = 0 |
| 7. | 50-foot walk test | 
 • >0 - 15 sec = 4 • >15 - 20 sec = 3 • >20 - 25 sec = 2 • >25 sec = 1 • 0, Unable = 0 |

Statistical Analysis Plan

| | | |
|-------------------------|---|---|
| 8. | Climb one flight of stairs | 
 • >0 - 5 sec = 4 • >5 - 10 sec = 3 • >10 – 15 sec = 2 • >15 sec = 1 • 0, Unable = 0 |
| 9. | Climb 4 flights of stairs (Number of flights climbed up and down) | 
 • 4 flights = 4 • 3 flights = 3 • 2 flights = 2 • 1 flights = 1 • Unable = 0 |
| Total mPPT Score | | Sum of all Item score values [0-36] |

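### Both tolerability endpoints and the AE-withdrawal table count leaving the study, so a patient who stops drug for an AE but does not leave because of one is missed

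*SAP*

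**What the plan says.** SAP 1.2.2 has two tolerability endpoints. Both count premature discontinuation from the study, the first for any reason and the second for adverse events: "Proportion of subjects (%) who prematurely discontinued from the study due to AEs". Protocol 2.3.1.2 and 9.8 word them the same way. SAP 8, which should say how they are analysed, has one sentence: "Tolerance is summarized with the safety analysis". Among the AE summaries in SAP 7.3, the only one tied to discontinuation is "AEs leading to withdrawal from the study".

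The same SAP separates stopping drug from leaving the study. SAP 2.1 says "Patients who discontinue study medication due to safety or tolerability reasons may continue in the study off drug" (protocol 3.1, 3.10.1, 3.12.4 and 7.1.7 have the same rule). SAP 2.1 also says that patients above a suicidality threshold will be "discontinued from treatment with study medication and will be referred to a psychiatrist", and points to protocol 6.1.5, where "Patients who are discontinued from treatment may continue their participation in the study and perform the scheduled visits and assessments, while off study drug". SAP 5.2 reports the two kinds of withdrawal side by side: "patients who withdraw from the treatment and study (and reasons for withdrawing) will be summarized using descriptive statistics".

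**The concern.** A tolerability endpoint is normally read as the share of patients who could not stay on the drug because of adverse events. Here it counts something else. A plan that encourages patients to remain under observation after stopping drug weakens the link between stopping drug and leaving the study. The better the sites retain such patients, the lower the AE endpoint reads relative to actual AE-driven drug stops.

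This touches the primary objective (SAP 1.1), and these two proportions are the only named tolerability endpoints. The study is uncontrolled and descriptive, so the counting rule largely determines the result. There would also be no SOC and preferred-term table explicitly based on the events that led patients to stop drug.

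**Working it through.** The plan states no discontinuation rate, so there is no figure to reproduce. The check has two parts.

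**1. Where each patient path is counted, read literally**

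| Path | Any-reason endpoint | AE endpoint | SAP 7.3 withdrawal table | Treatment withdrawal in SAP 5.2 |
|---|---|---|---|---|
| Stops drug for an AE, stays to study end | no | no | no | yes |
| Stops drug for an AE, later leaves only for another reason | yes | no | no | yes |
| Stops drug for an AE, leaves at least partly because of an AE | yes | yes | yes | yes |

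The third row uses protocol 7.1.7: if an AE is among several reasons for leaving, the termination page records an AE. That section makes an exception for an AE that is not itself severe enough to end participation but needs a prohibited medication.

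The first two rows can arise under the documents' own rules:
- Hypokalemia: protocol 3.10.1 withdraws some patients from drug and asks them to stay in the study. Protocol 7.3 makes a confirmed laboratory abnormality that causes drug cessation an AE.
- Suicidality: protocol 6.1.5, 7.1.1 and 7.8.1 stop drug and allow the patient to stay. Protocol 7.1.6 says the patient leaves both study and drug. Whether such a patient enters the endpoint depends on which passage a site follows.

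**2. Size, on assumed values**

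None of these inputs is in the documents:
- q = share of patients who stop drug for an AE
- f = share of those who do not leave the study because of an AE
- e = share of all patients who leave for an AE without an AE-driven drug stop

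Endpoint = q(1 − f) + e. Patients not captured = N·q·f. Net understatement = q·f − e. N is up to 300 (protocol 9.1) or up to 650 (SAP 2.4).

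f can be split as f = r + (1 − r)g, where r is the share of AE drug-stoppers who stay to completion and g is the share of the rest who leave for a non-AE reason. With r = 0 and g = 0.2, f = 0.2, so some patients are missed even if nobody stays to the end. With r = 0.5 and g = 0, f = 0.5. With r = 0.5 and g = 0.2, f = 0.5 + 0.5 × 0.2 = 0.6.

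With e = 0:

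| q | f | Endpoint reads | Not captured of 300 | Not captured of 650 |
|---|---|---|---|---|
| 10% | 0 | 10% | 0 | 0 |
| 10% | 0.2 | 8% | 6 | 13 |
| 10% | 0.5 | 5% | 15 | 32.5 |
| 10% | 0.6 | 4% | 18 | 39 |
| 10% | 1 | 0% | 30 | 65 |
| 20% | 0 | 20% | 0 | 0 |
| 20% | 0.2 | 16% | 12 | 26 |
| 20% | 0.5 | 10% | 30 | 65 |
| 20% | 0.6 | 8% | 36 | 78 |
| 20% | 1 | 0% | 60 | 130 |

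The error can also run the other way. A patient who leaves for an AE after treatment has ended adds to e. So does one taken off drug for a prohibited medication who stays (protocol 5.3) and later leaves for an AE, although that rule is worded for a randomized phase that this study does not have. With q = 10%, f = 0.5 and e = 1%, the endpoint reads 0.10 × 0.5 + 0.01 = 6%, a net understatement of 5 − 1 = 4 percentage points. The sign reverses only if e exceeds q·f, here 5%.

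**The case against.** The strongest reply is that the main number is already planned. SAP 5.2 gives treatment withdrawals with reasons. If AE is a recorded reason, the count and percent stopping drug for an AE will appear there, and every AE on or after the first dose is tabulated under SAP 7.3 anyway. Protocol 9.7.2 also plans listings of AEs leading to withdrawal, without limiting them to exit from the study. SAP 7.3 does not repeat these listings, but silence is only weakly a difference that would let the SAP override the protocol. Protocol 7.1.7 uses withdrawal for both study and treatment and then requires the termination page. If that page feeds the endpoint, drug-only stops may already be counted. The supplied protocol plans 300 patients and the SAP 650, so the detailed examples may come from a different version. The sizes above are assumptions, and no statistical test is affected.

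Much of this stands as a limit. The information is partly recoverable, the CRF cannot be seen, and the examples are illustrations. None of it supplies a tolerability measure or an SOC and preferred-term summary explicitly based on stopping drug. The disposition count is on the ITT set (SAP 5.1), has no event detail and is not labelled a tolerability result. The termination-page ambiguity means two programmers could derive different endpoint values, which supports stating the rule. The version difference does not reach the core, which rests on SAP 1.2.2, 2.1, 5.2 and 7.3 alone.

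**Conclusion.** The concern holds. On a literal reading of the SAP, an AE-driven drug stop without an AE-driven study exit is in neither the AE tolerability endpoint nor the AE-withdrawal table. The endpoint will generally understate AE-driven drug discontinuation, by q·f − e. On assumed values of q = 10%, f = 0.5 and e = 0 it reads 5% instead of 10%. The possible range runs from no effect (f = 0, e = 0) to none of the AE drug stops counted (f = 1), and the documents cannot narrow it. The direction is likely but not certain. Confidence is moderate because the CRF rule for a drug-only stop is not stated. The point should be fixed because it affects the primary objective and can be closed cheaply. It does not invalidate the study, since disposition recovers part of the loss.

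**What to change.** Keep both protocol endpoints and their rank, and make these changes to the SAP before database lock:

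- **SAP 8:** add the number and percent who prematurely discontinued study drug, for any reason and due to AEs, on the safety analysis set.
- **SAP 7.3:** add an SOC and preferred-term table of AEs leading to discontinuation of study drug, derived from the action taken on study drug that protocol 7.1.2 already has recorded for each AE.
- **Definition:** state which CRF record defines discontinuation from the study and how a drug-only stop is entered on the termination page.
- **SAP 10:** list the addition; it now reads "There are no changes to analyses specified in the study protocol".

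Protocol section 9 leaves additions to the analyses to the SAP, so these changes need no new endpoint in the protocol. The cost is SAP wording, two summary lines and one table, plus a possibly less favourable discontinuation rate. No new data are needed.

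Separately, the sponsor should reconcile protocol 7.1.6 with 6.1.5, 7.1.1, 7.1.7 and 7.8.1 on whether a suicidality AE ends study participation or only drug treatment, because endpoint status depends on it. That is a protocol clarification, and this review takes no view on which rule should apply.

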1.2.3. Efficacy Endpoints

Efficacy endpoints for this study include the following:

- Unified Huntington's Disease Rating Scale – Total Motor Score (UHDRS-TMS)
- Modified Physical Performance Test (mPPT)
- Unified Huntington's Disease Rating Scale - Total Functional Capacity (UHDRS-TFC)
- Short Form 12 (SF-12) questionnaire (acute version)
- Problem Behaviors Assessment-Short form (PBA-s) (also part of safety assessments)

Statistical Analysis Plan

- Quantitative motor (Q-motor) assessments (up to 104 weeks; not applicable for newly enrolled patients after Global Amendment 02)

2. STUDY DESIGN

[figure not shown]
2.1. General Design

This is a multicenter, open-label study to evaluate the safety, tolerability, and efficacy of pridopidine treatment at a dosage of 45 mg bid in adults with HD. The study will consist of a screening period up to 2 weeks, followed by an open-label treatment period.

The assessments and procedures performed during each study visit are detailed in Section 3.12 of the protocol.

Up to 650 patients from the PRIDE-HD, Open PRIDE-HD, Open-HART, or future safety and efficacy clinical trials of pridopidine studies are planned to be enrolled to receive a total daily dose of 90 mg pridopidine (45 mg bid) for the duration of the study.

If medically necessary (eg following discussion with the medical monitor), the patient may be allowed to de-escalate to a dose of 22.5 mg bid. The start date and reason for de-escalation will be entered into the electronic case report form (eCRF).

In addition, patients who have already completed their defined study period under Open PRIDE-HD global or local amendments and have discontinued treatment with pridopidine can be re-enrolled and re-enter the Open PRIDE-HD study. A repeat, 2nd screening and baseline visit will be scheduled after completion of the End of Study (EoS) visit. These patients will complete the repeated (2nd) screening and baseline visit assessments (including meeting all eligibility criteria, see procedures for V1 and V2), and undergo a 1-week titration period and resume attendance of the study visits from the point at which they exited.

All patients will be treated with study drug during the course of the study. After the 1 week titration period, patients will be seen at weeks 4, 12, 26, 52, 78, and every 26 weeks thereafter. An EoS follow-up visit will take place 2 weeks after end of treatment visit. Safety evaluation telephone calls will be performed at weeks 18, 38, and every 26 weeks thereafter. The alternating safety visits and telephone contacts (TCs) result in a safety assessment frequency of approximately every 3 months throughout the entire study duration. The safety TCs must be conducted by the study investigator. During these phone calls, inquiries about adverse events, concomitant medication (including changes in use of benzodiazepines and antidepressants), changes in use of alcohol and illicit drugs, C-SSRS, and an abbreviated PBA-s (a subset of PBA-s questions on depressed mood, suicidal ideation, anxiety, irritability, loss of motivation, and obsessive-compulsive behaviors) will be conducted.

During the TCs, if the patient receives a score of 0 on the C-SSRS and PBA-s suicidal ideation assessments, the subsequent safety TCs will remain as scheduled as long as the scores of 0 are unchanged. If the patient receives a score of 1 or 2 on the C-SSRS or PBA-s suicidal ideation assessments, the safety TCs will be conducted every 4 weeks to monitor the patient's status until the scores change to 0 (after which the frequency of safety TCs will revert back as scheduled, as described above). Patients with a C-SSRS ideation score of 3 and above or a PBA-s suicidality

score of 3 and above, and all patients with C-SSRS suicidal attempts or acts (behavior), will be discontinued from treatment with study medication and will be referred to a psychiatrist for further evaluation and assessment, and handled as described in Section 6.1.5. of the protocol.

For patients with a C-SSRS or PBA-s score of 1 or 2, if in the judgment of the investigator, the patient is not in good mental health during an in-clinic visit or safety TC, the frequency and the methods for monitoring may be changed (ie, more frequent visits or TCs may be added as deemed necessary, or the patient can be referred to a psychiatrist for additional evaluation and treatment and will be monitored until recovery or their condition stabilizes, in accordance with the instructions provided in Section 6.1.5 and Section 7.8.1 of the protocol.

Patients who discontinue study medication due to safety or tolerability reasons may continue in the study off drug and perform the scheduled visits and assessments.

[figure not shown]
Patients who withdraw from the study will have the early termination procedures and assessments performed at their final visit.

An independent internal safety committee will oversee the study (see Section 3.6.1 of the protocol).

Digital Health Sub-study (optional participation):

Motor symptoms can be objectively assessed in HD patients using different quantitative motor assessments.

Objective motor assessments aim at improving the limited sensitivity observed with categorical clinical rating scales, and reducing the intra- and inter-rater variability, as well as potential placebo effect observed in scales such as the UHDRS. Improved sensitivity for early-stage clinical studies of efficacy of a new drug on motor dysfunction is expected with objective assessments and may support early go/no go decisions in smaller cohorts of patients.

Study procedures and assessments are outlined in Table 1 of the sub-study protocol.

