4.5. Study Days and Visits

Study days are numbered relative to the first day of study drug administration. The start of treatment (Day 1) is defined as the date on which a patient takes the first dose of study drug, as recorded on the study drug diary. Days will be numbered relative to treatment start (ie, ..., -2, -1, 1, 2, ...; with day 1 being the first day of study drug administration and day -1 being the day before the first day of study drug administration).

For efficacy and safety by-visit analyses, data collected at postbaseline scheduled visits will be included using their scheduled visit, data collected at postbaseline unscheduled visits will be included and assigned to their corresponding scheduled visit, and data collected at early termination visits will be included and assigned to the next scheduled visit. After the assignments are made, if there is a scheduled and unscheduled visit at the same visit, the scheduled visit will be used in the analysis.

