6.2. Efficacy Endpoint and Analysis

The efficacy endpoints are as follows:

- UHDRS-TMS change from baseline to each visit that this is measured.
- mPPT total score change from baseline to each visit that this is measured.
- UHDRS-TFC change from baseline to each visit that this is measured.
- SF-12 total score change from baseline to each visit that this is measured.
- PBA-s total score change from baseline to each visit that this is measured.
- Q-motor assessments (digitomotography, dysdiadochomotography, manumotography and choreomotography, and pedomotography) change from baseline to each visit that this is measured.

All efficacy endpoints will be summarized for actual values and changes from baseline to each visit using descriptive statistics.

PBA-s domain scores will also be summarized for actual values and changes from baseline of this study to each visit using descriptive statistics.

No formal inferential statistics will be applied to the efficacy endpoints. Efficacy analyses will be considered exploratory.

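### Re-entered patients keep their old visit numbering and are pooled with everyone else, so by-visit summaries after the exit point mix uninterrupted treatment with treatment split by an off-drug gap

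*SAP*

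**What the plan says.** SAP 2.1 describes re-entry. Patients who have finished their defined period and "have discontinued treatment with pridopidine can be re-enrolled and re-enter the Open PRIDE-HD study". On timing it adds: "A repeat, 2nd screening and baseline visit will be scheduled after completion of the End of Study (EoS) visit". These patients must meet all eligibility criteria again, titrate for one week, and then "resume attendance of the study visits from the point at which they exited". The end-of-study visit itself comes after a drug-free interval: "An EoS follow-up visit will take place 2 weeks after end of treatment visit". The visit grid in the same section is that "patients will be seen at weeks 4, 12, 26, 52, 78, and every 26 weeks thereafter".

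SAP 4.5 sets the time axis of the tables: "data collected at postbaseline scheduled visits will be included using their scheduled visit". Study days run from the first dose. The section has no reset, second origin or flag for a patient who starts twice.

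SAP 4.2 takes the baseline for PRIDE-HD patients as the last value before the first dose in this study, and for Open-HART patients as the last value before the first dose in Open-HART. It does not mention the repeat baseline visit.

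SAP 6.1 and 7.1 present summaries for all patients together. SAP 6.2 states: "All efficacy endpoints will be summarized for actual values and changes from baseline to each visit using descriptive statistics". SAP 7.4 to 7.6 do the same for laboratory tests, vital signs and ECG variables. No section separates re-entered patients, ends their series at first exit, or limits the gap.

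**The concern.** Each rule is reasonable alone, but together they put two treatment histories under one visit label. A patient who left at Week 52, came off drug and restarted next appears in the Week 78 row beside patients treated for 78 weeks without a planned break. A patient who left at Week 104 next appears at Week 130.

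This matters because long-term effect is a secondary objective and the study has no comparator. Change from baseline over time is the only efficacy evidence it will produce. Huntington's disease is progressive, so time off drug adds progression to a change measured from the original baseline, and the visit label does not show that extra time. In the by-visit laboratory, vital-sign and ECG means and shifts, values from re-screened patients who recently restarted are averaged with values from patients who never left. A reader of the late rows cannot tell how much of either is present.

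**Working it through.** The plan states no figure to reproduce: the study is descriptive, with no power, alpha or effect size. The check is timeline arithmetic, followed by an illustration on assumed inputs.

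**Inputs from the documents**
- Visit after re-entry: the next one on the original grid (SAP 2.1).
- Label used in tables: the nominal visit (SAP 4.5).
- Smallest nominal gap: 2 weeks from end of treatment to end of study. Re-screening follows, and for screening SAP 2.1 says: "The study will consist of a screening period up to 2 weeks, followed by an open-label treatment period". If re-screening follows promptly, the gap is about 2 to 4 weeks. No maximum is stated.
- Exit points: Protocol 1.8 describes a 52-week extension to a total of 104 weeks, so Week 52 and Week 104 are both plausible.

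**Assumed inputs (not in the documents)**
- Longer gaps of 26 to 52 weeks.
- Progression of 2 to 4 TMS points per year.
- Re-entered patients supply 20 to 40% of the values in a cell.

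**Step 1: what the label means.** With label L and gap g in weeks, cumulative on-drug time is about L, and time since first dose is L + g. In both examples only the last 26 weeks are unbroken (78 − 52, or 130 − 104).

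| Gap (weeks) | Weeks since first dose at label 78 (exit at 52) | Weeks since first dose at label 130 (exit at 104) |
|---|---|---|
| 2 | 80 | 132 |
| 4 | 82 | 134 |
| 26 | 104 | 156 |
| 52 | 130 | 182 |

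**Step 2: the pooled cell.** With share f, mean time since first dose is L + f × g. At label 78:
- Gap 2 to 4 weeks: 78 + 0.2 × 2 = 78.4 to 78 + 0.4 × 4 = 79.6 weeks.
- Gap 26 to 52 weeks: 78 + 0.2 × 26 = 83.2 to 78 + 0.4 × 52 = 98.8 weeks.

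**Step 3: effect on mean TMS change from the original baseline.** Individual shift = rate × g / 52. Mean shift = individual shift × f.

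| Gap (weeks) | Rate (points/year) | Individual shift | Share | Mean shift |
|---|---|---|---|---|
| 2 | 2 | 2 × 2/52 = 0.077 | 0.2 | 0.015 |
| 4 | 4 | 4 × 4/52 = 0.308 | 0.4 | 0.12 |
| 26 | 2 | 2 × 26/52 = 1.0 | 0.2 | 0.2 |
| 52 | 4 | 4 × 52/52 = 4.0 | 0.4 | 1.6 |

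A higher TMS is worse, so the shift is towards apparent worsening. The illustration treats the gap only as added disease time and assumes no separate effect of stopping or restarting.

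**Step 4: dependence on baseline.** The shift in Step 3 arises because SAP 4.2, read literally, measures change from before the first dose. Measured from the repeat baseline, progression during the gap drops out of the change score. The visit label and the baseline must therefore be settled together.

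**The case against.** Much of the case on the other side stands.

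- **The label is right on one scale.** Someone might infer that Week 78 is simply wrong, because the patient has had only 26 weeks of renewed treatment. The documents do not support that. The 52 weeks before exit count too, so the label matches approximate cumulative on-drug weeks, and SAP 4.5 never says that a label means calendar time or unbroken treatment. But the SAP does not name on-drug time as its scale either.
- **The effect may be trivial.** Prompt re-entry gives a gap of 2 to 4 weeks and a mean shift of at most about 0.12 points under the assumptions above.
- **Comparison with the drug effect is tempting but invalid.** Someone might set 1.6 points against the improvement of about 3 points in Protocol 1.5.1. That figure is relative to placebo, from trials of 12 and 26 weeks (Protocol 1.3.2.2). Change from baseline here contains progression for every patient.
- **Safety events after restart are not hidden.** SAP 7.3 counts adverse events from the first dose onward. SAP 7.4 and 7.5 screen all postbaseline laboratory and vital-sign values for potential clinical significance. SAP 7.6 uses the worst postbaseline finding for the overall ECG result. Only by-visit means and shifts are affected.
- **By-visit tables were never restricted to unbroken treatment.** Patients may stay in the study off drug (SAP 2.1), and temporary interruptions are allowed (Protocol 5.5). That limits what any fix can claim. It does not justify another unmarked mixture.
- **A later amendment may limit the gap.** The supplied protocol, with Amendment 02, has no re-entry provision, so the SAP appears to follow a version not supplied. The SAP nevertheless governs the tables and has no handling rule.

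**Conclusion.** The point holds as a matter of reporting. Under SAP 2.1, 4.5, 6.1 and 7.1, by-visit summaries after the exit point pool uninterrupted and gap-split treatment. The nominal week understates time since first dose by the length of the gap. With the original baseline, long-term change also includes off-drug progression.

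The mixing is certain if anyone re-enters and contributes data, because re-entry requires having stopped drug and completed the end-of-study visit. Its size is unknown. The range runs from negligible (0.015 points) to material (1.6 points) on the TMS mean, and depends entirely on the assumed progression rate, share and gap. No error rate or decision rule is affected, since all efficacy analyses are exploratory and descriptive. The change is still worth making, because the uncontrolled time course is the study's only efficacy evidence and the remedy is inexpensive.

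**What to change.** In SAP 4.5:

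- Add a treatment-period flag derived from recorded dose dates.
- End the main by-visit series for re-entered patients at their first exit, and call it the first treatment period. It should not be called uninterrupted treatment, because patients who stay in the study off drug or interrupt temporarily remain in it as now.
- Summarise data after re-entry separately, by weeks since restart, with change from the repeat baseline. Change from the original baseline may be shown alongside. Amend SAP 4.2 to match.
- Report the number of re-entered patients and the distribution of their gaps, so that readers can judge the size directly.

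No new data or visits are needed, and SAP 2.5.2 allows amendment before database lock. The cost is one derived variable, one extra and possibly sparse set of tables, and fewer patients in the late-visit cells of the main series.
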